Overview of the Trial: This study is a randomized trial of the video in 50 AYAs with advanced cancer and their caregivers that will assess preferences for care in advanced cancer and concordance rate of preferences between dyad. We will randomly assign dyads to one of two ACP modalities: 1. the ACP video decision aid (intervention), or 2. Usual care. Patients' and caregivers' knowledge, preferences (goals of care, CPR, ventilation), and decisional conflict be assessed before and after exposure to the video or control ACP modality. Telephone-based interviews will be conducted at 3 months to assess patients' and caregivers' preferences, ACP conversations with caregivers and clinicians, and the medical record will be queried to examine ACP documentation. The primary outcome is AYA and caregiver concordance regarding treatment preferences for advanced cancer (Aim 1). Secondary outcomes include knowledge, preferences, decisional conflict, and ACP engagement (Aims 1 and 2). We will also explore the stability of preferences, presence of ACP conversations and documentation after 3 months (Aim 2). We hypothesize that the video decision aid better informs patients and their caregivers and leads to more informed decision making.

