6.0 Study Timelines

Participants enrollment in the study will last the course of 3 months with one inperson study visit and one phone-based interview. The study entails a one-time 30-40 minute in-person visit or over Zoom where participants will be randomized to the video aid intervention or information sheet control. Around three months following this initial visit, participants will complete a 5-10 minute follow-up phone-based interview. This follow-up interview will be audio recorded with the participants' knowledge and transcribed for analysis. Participants will have consented to be audio recorded during the informed consent process. All recordings will be de-identified. Given the number of AYA patients typically treated at this institution, we anticipate the study to span 2 years, including 3month data collection tools preparation and survey training, 16 months rolling recruitment, surveying, and 3-month follow-up, 2 months data cleaning, analysis, and manuscript preparation. This timeline will continue to be updated given changes to recruitment/enrollment strategies in the setting of COVID-19.

7.0 **Procedures Involved**

Study design, randomization, intervention, and control arm: We will conduct a randomized controlled trial in 50 AYA with advanced cancer and their caregivers who

will be randomized as dyads to either the video (intervention) or usual care (control) (Figure 1). After enrollment, we will collect the following information from the caregiver: full name, date of birth, zip code, and gender for the purposes of reporting to the NCI and subject level registration.

Figure 1. Data collection time periods for the proposed study.

The interview script for the encounter with participants is provided in Appendix C. Following completion of the pre-intervention questionnaire (Appendix D), the RA will provide a brief explanation of the three types of care (life-prolonging, selective, comfort) and the subjects will be randomized to intervention or usual care. Patients and caregivers in the control group will only receive the verbal description of the three types of care (Appendix C, page 1).

Randomization: We will use a central, computer-generated simple randomization design stratified by race and ethnicity for even recruitment in both arms of the study.

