Data elements of survey questionnaire: We are interested in studying the influence of the video compared to enhanced usual care on medical care options and concordance rate with 50 AYA with advanced cancer and their caregivers. To assess study outcomes, data will be collected, to the extent possible, using validated tools. Table 1 outlines the data elements that will be obtained from both patients and caregivers. The audio recording and de-identified transcripts will be stored in a stored location on a secured network only accessible to the study team. The audio recording and de-identified transcripts will be stored in a stored location on a secured network only accessible to the study team.

Sociodemographics: Data on sociodemographics will include age, gender, race, ethnicity, health insurance, education, marital status, religion, and religious attendance. (Appendix D, page 1-2, questions 1-8).

Preferences: Patients and caregivers will be asked for their goals-of-care preference (lifeprolonging, selective, comfort, or Unsure), CPR preference (Yes, No, or Unsure), and ventilatory support (Yes, No, or Unsure) at baseline, and then again immediately after watching the video or reviewing the informational sheet (Appendix D, page 4, question 1-3; Appendix H, page 1, question 1-3) and then we will contact all patients after 3 months by telephone to ask for their preferences.(11, 13, 20) (Appendix I, page 2-3, question 1-3). We will also have an open-ended question for those patients who change their preferences from the initial post-video or control survey ("Can you explain why you have changed your preference from the one stated three months ago?"). AYAs and caregiver concordance of preferences (i.e., the same preference) is our primary outcome.

Knowledge: We will ask five true/false questions and one multiple choice question regarding knowledge of goals-of-care options which were used and validated in our previous studies.(11, 13, 20) (Appendix D, page 6; Appendix H, page 3).

Decisional conflict: We will measure decisional conflict, which attempts to measure uncertainty regarding decision making.(52) The Decision Conflict Scale is a wellvalidated and commonly used tool, we will use the 4-item SURE scale for ease of use and to reduce burden on the participant.(52) (Appendix D, bottom of page 4, questions 1-4; Appendix H, bottom of page 1, questions 1-4).

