during the face-to-face or virtual interviews. The RA will collect baseline data, randomize patients and caregivers as a dyad to either the video or control arm via concealed envelopes, and administer the intervention. After this baseline interview and randomization, the RA will collect the remaining outcomes data regarding preferences, knowledge, and decisional uncertainty from both the patient and caregiver. For those participants randomized to the video intervention, they will also be asked questions regarding the usefulness of the video and their comfort with the video. If patients express interest in creating their own video, RA's may provide an information sheet to guide them through the process (Appendix J). Both patients and caregivers will be contacted at 3 months and assess their preferences and ACP conversations at that time. These phonebased interviews will be conducted independently to reduce influence on the outcome of concordance and will be audio recorded for later analysis.

Table 1: Data Element and Sources									
		SOURCE							
Data Collected	Purpose	Tool	By Whom	From	When	Note			
1. Eligibility screen									
Advanced Cancer	target sub-population identification, covariate		RA, PO	EHR	Daily	HIPAA waiver			
Cognitive Assessment	screening	SPMSQ	RA	interview	Outpatient/Vir tual				
2. Baseline Assessment									
Preferences	2º outcome		RA	interview	Outpatient/Vir tual				
Knowledge	2º outcome		RA	interview	Outpatient/ Virtual				
Randomization followed by video intervention or enhanced usual care									
3. Post-video or informational sheet									
Preferences	2º outcome		RA	interview	Outpatient/ Virtual				
Preference concordance	1º outcome		RA	interview	Outpatient/ Virtual				
Knowledge	2º outcome		RA	interview	Outpatient/ Virtual				
Decisional conflict	2º outcome	DCS	RA	interview	Outpatient/ Virtual				
ACP engagement	2º outcome	ACPE	RA	interview	Outpatient/ Virtual	AYA only			
Comfort with video	2º outcome		RA	interview	Outpatient/ Virtual	Video arm			
4. Follow-up at 3 months									
Preferences	2º outcome		RA	telephone					
ACP conversations	2º outcome		RA	telephone					

KEY: RA: Research Assistant; PO: Primary Oncologist; EHR: Electronic Health Record; SPMSQ: Short Portable Mental Status Questionnaire; DCS: Decisional Conflict Scale; ACPE: Advance Care Planning Engagement Questionnaire.

DATA ANALYSES

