Aim 1: H1: AYA with advanced cancer and caregivers randomized to the video will have higher concordance between patients and caregivers (Primary Outcome), and more likely to have higher knowledge, make decisions for less burdensome care (i.e., limited or comfort care, no CPR, no ventilatory support), have lower decisional conflict, and engagement, than those randomized to the control group. Preference concordance between patient and caregiver will be treated as a dichotomized variable and compared between the two study arms using a chi-square test. We will conduct separate analyses for patients and caregivers for secondary outcomes. Knowledge score, decision conflict scale, and ACP engagement will be considered as continuous variables. We will use twosample t-tests or Wilcoxon rank sum tests, whichever more appropriate, to compare the distribution between the two study arms. Chi-square tests will be used to compare the proportion of patients/caregivers choosing less burdensome care between the two study arms. We will explore the effect of patient characteristics (age, sex, etc.) in choosing less invasive care using a logistic regression model. In this study, we will treat sex as selfreported gender and will conduct a sex-based analysis of intervention effects to explore sex as a biological variable. *Power analysis*: Assuming 50% of control arm achieve preference concordance between patients and caregivers, the study will have 80% power to detect a 41% difference (50% vs. 89%) in concordance. Assuming 68% of control patients/caregivers choose non-life prolonging care, the study will have 82% power to detect a 31% difference (68% vs. 99%) in preferences between the two arms. For the continuous outcomes (knowledge, decisional conflict, ACP engagement), the study will have 80% power to detect an effect size of 0.81 with 25 subjects per group.

Aim 2: *H2.* Patients randomized to the video will have more ACP conversations and documentation after 3 months. We will treat conversations and documentation as continuous variables. Assuming 50% of controls achieve ACP conversations/documentation between baseline and three-month follow-up, the study will have 81% power to detect a 27% difference (50% vs. 77%) between the two study arms.

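### Dyad concordance before randomisation can be derived from data already collected, but it is never derived, reported or used in the primary comparison, so chance baseline imbalance stays uncorrected and precision may be lost

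*Combined protocol and SAP*

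**What the plan says.** **When preferences are collected.** The overview of the trial (Section 2.0) says that knowledge, preferences and decisional conflict will "be assessed before and after exposure to the video or control ACP modality". The Preferences paragraph of Section 8.0 has patients and caregivers give their goals-of-care, CPR and ventilation preferences "at baseline, and then again immediately after watching the video or reviewing the informational sheet". Section 7.0 puts the first questionnaire ahead of everything else: "Following completion of the pre-intervention questionnaire (Appendix D), the RA will provide a brief explanation of the three types of care", and the dyad is then randomised. The data collection protocol in Section 8.0 gives the same order: "The RA will collect baseline data, randomize patients and caregivers as a dyad to either the video or control arm via concealed envelopes".

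**The primary outcome.** Section 8.0 states: "AYAs and caregiver concordance of preferences (i.e., the same preference) is our primary outcome". Table 1 lists preference concordance only in the post-exposure block, as the primary outcome. The baseline block lists preferences as a secondary outcome and has no concordance row.

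**The analysis.** Data Analyses, Aim 1: "Preference concordance between patient and caregiver will be treated as a dichotomized variable and compared between the two study arms using a chi-square test". The one covariate model in that section concerns a different endpoint: "We will explore the effect of patient characteristics (age, sex, etc.) in choosing less invasive care using a logistic regression model". Randomisation (Section 7.0) is stratified by race and ethnicity only. The work on stability of preferences and on reasons for change looks at three months, and the missing-data section adds no baseline adjustment.

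**The concern.** Allocation cannot influence a dyad's agreement before randomisation, and that agreement may predict its agreement an hour later. Leaving it out has three consequences.

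- **Chance imbalance.** With 25 dyads per arm, the arms can differ noticeably in concordance before anyone sees the video. The crude test carries part of that difference into the primary result, in either direction.
- **Precision.** If baseline and post-exposure concordance are correlated, a stratified comparison has more power at the same sample size.
- **Interpretation.** The objectives speak of the video leading to more congruent decisions. A dyad that agreed beforehand and still agrees is recorded the same way as one that moved into agreement, and no planned table separates them. A pilot meant to support a larger trial would want that split.

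**Working it through.** **Inputs from the documents.** 25 dyads per arm (Section 1.0, Aim 1); 50% concordance in controls and 89% with the video, power 80% (Data Analyses, Aim 1).

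**Assumptions, because the documents are silent.** Two-sided alpha 0.05; baseline concordance 50% (set equal to the planned control rate); baseline-to-post correlation r = 0.3, 0.5 or 0.7.

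**Step 1. The plan's own power.** Exact binomial enumeration, 25 vs 25, 50% vs 89%: Yates-corrected chi-square 80.1%, Fisher 80.3%, uncorrected chi-square 89.1%. The stated 80% is reproduced by a corrected or exact test. (The text calls this a 41% difference, but 89 - 50 = 39. At 50% vs 91% Yates would give 85.7%, so the 80% belongs to 50% vs 89%. This does not affect the point.)

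**Step 2. Size of chance imbalance at baseline.** SD of the between-arm difference = sqrt(2 x 0.5 x 0.5 / 25) = 0.141, or 14 points. By exact convolution of two Binomial(25, 0.5) variables:
- difference of at least 4 dyads (16 points), either direction: 32.2%
- difference of at least 5 dyads (20 points), either direction: 20.3%; favouring the video: 10.1%

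**Step 3. What passes into the result when the video does nothing.** With 50% concordance at both times, a concordant dyad stays concordant with probability s = 0.5 + 0.5r, and a discordant dyad becomes concordant with probability c = 0.5 - 0.5r. A baseline difference d produces an expected post-exposure difference of (s - c) x d = r x d. Among trials with at least 20 points in favour of the video, the mean of d is 24.8 points (same enumeration). So:
- r = 0.3: 0.3 x 24.8 = 7 points
- r = 0.5: 0.5 x 24.8 = 12 points
- r = 0.7: 0.7 x 24.8 = 17 points

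**Step 4. Rejection rates in those trials.** Simulation with no video effect. The Mantel-Haenszel (MH) statistic, without continuity correction, is [sum(a - n1 m / t)]^2 / sum[n1 n0 m (t - m) / (t^2 (t - 1))] over the two baseline strata. Here a is the number of video dyads concordant after exposure, n1 and n0 are the arm sizes, m is the total concordant and t is the stratum size.

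| r | Uncorrected chi-square | Yates chi-square | Stratified MH |
|---|---|---|---|
| 0.3 | 9% | 5% | 4-5% |
| 0.5 | 14% | 8% | 4-5% |
| 0.7 | 21% | 12% | 4-5% |

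**Step 5. Power.** The stratified figure depends slightly on how the effect is spread over the strata. At 50% vs 89% it is shown for a constant odds ratio. At 50% vs 80% the lower figure is for an equal proportional cut in discordance and the higher for a constant odds ratio.

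| r | 50% vs 89%: uncorrected | 50% vs 89%: MH | 50% vs 80%: uncorrected | 50% vs 80%: MH |
|---|---|---|---|---|
| 0.3 | 89% | 90% | 64% | 63-64% |
| 0.5 | 89% | 93% | 64% | 68-70% |
| 0.7 | 89% | 96% | 64% | 76-80% |

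The like-for-like comparison is MH against the uncorrected chi-square, since neither has a continuity correction. The gap to the plan's 80% also contains the effect of that correction.

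**Step 6. Wider assumptions.** With baseline concordance of 30-50% and 70-95% of concordant control dyads staying concordant, an imbalance of at least 20 points occurs in 16-20% of trials. When it favours the video, the false shift is 7 to 22 points. The uncorrected chi-square then rejects in 9-29% of such trials, against 2-5% for MH. Stratified power is 89-98% at 50% vs 89% and 63-89% at 50% vs 80%.

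**The case against.** The planned analysis answers the hypothesis as written. H1a compares the level of congruence between arms, and the outcome is having the same preference, not a change. A reader might infer that dyads already in agreement bias the comparison. They do not: they count alike in both arms, randomisation equalises their expected share, and the control arm supplies the counterfactual. This part of the objection stands in full.

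A reader might also infer that ignoring baseline raises the overall false-positive rate, because the uncorrected chi-square runs at about 6.5% here and MH at about 5%. That excess is the small-sample behaviour of the uncorrected test. It is much the same at every correlation, and Yates gives 3.3%. It is no argument for adjustment.

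The rates in Step 4 apply to only 10% of trials, selected because chance favoured the video. If the test is run with the Yates correction, which matches the plan's power figure, they are roughly halved and sit at the nominal level for r = 0.3.

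Nor do the documents show that baseline concordance predicts strongly. The first answers are given before the types of care are explained to either arm, so preferences may move in both. At r = 0.3 the power gain is about nil.

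What survives is a trial-specific case for adjustment: the variable is already collected before allocation, the trial is small, and the downside is about one point of power.

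**Conclusion.** The point holds as a recommended improvement, not as an error in the test. The planned chi-square is valid and unbiased on average. It leaves chance imbalance uncorrected, gives up precision if baseline and post-exposure concordance are correlated, and hides whether agreement was maintained or achieved.

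On the stated assumptions, one trial in five starts with the arms at least 20 points apart. When that favours an ineffective video, the observed difference is inflated by 7 to 17 points on average. The power gain from stratifying is about 1 to 7 points at the planned 50% vs 89%. At 50% vs 80% it ranges from about nil to 16 points.

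The omission itself is certain from the text. The size of the benefit is not, because the baseline rate, the correlation and alpha are all assumed.

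**What to change.** 1. State which preference items (goals of care, CPR, ventilation) define concordance and how an 'Unsure' answer counts. The documents do not say, and the rule is needed for the post-exposure value in any case.
2. Apply the same rule to the Appendix D answers, add a baseline preference concordance row to block 2 of Table 1, and report it by arm.
3. Prespecify as the primary comparison a Mantel-Haenszel test stratified by baseline concordance (yes/no), or a logistic model adjusted for it, exact or penalised if cells are sparse.
4. Report post-exposure concordance by arm within each baseline stratum.
5. Keep the crude chi-square as a supporting analysis.

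This should be written before outcome data are seen, since adjusting only after an imbalance appears would look selective. The cost is one derived variable and some analysis wording. It needs no new data, visit, participant or increase in sample size. If the correlation is weak, the loss of power is at most about one point.

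### Randomisation is stratified by race and ethnicity, but no named between-arm test uses the strata, so chance imbalance goes uncorrected or, if the arms are balanced within strata, the plain test can become conservative

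*Combined protocol and SAP*

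**What the plan says.** Section 7.0 (Randomization) states: "We will use a central, computer-generated simple randomization design stratified by race and ethnicity for even recruitment in both arms of the study". Section 8.0 (data collection protocol) makes the dyad the unit: the research assistant will "randomize patients and caregivers as a dyad to either the video or control arm via concealed envelopes". No block size, number of strata or stratum levels are given. Nor is it said whether the patient's or the caregiver's race and ethnicity defines the stratum. Both variables are among the sociodemographic items collected in Section 8.0.

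Under Data Analyses, Aim 1, the plan says of the primary outcome: "Preference concordance between patient and caregiver will be treated as a dichotomized variable". It is then "compared between the two study arms using a chi-square test". For the continuous secondary outcomes: "We will use twosample t-tests or Wilcoxon rank sum tests, whichever more appropriate". For the preference outcome: "Chi-square tests will be used to compare the proportion of patients/caregivers choosing less burdensome care between the two study arms". The one model with covariates is exploratory and concerns a different outcome: "We will explore the effect of patient characteristics (age, sex, etc.) in choosing less invasive care using a logistic regression model". It does not name race or ethnicity. Aim 2 names no between-arm test.

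**The concern.** A factor important enough to be the only stratification variable would normally appear in the primary analysis. Here it appears in none of the named comparisons. What that costs depends on how the allocation list is built.

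- **Simple randomisation within strata, no blocks.** The arms can differ by chance in their race and ethnicity mix. If the factor is related to concordance, a plain chi-square test does not correct for that difference.
- **Arms balanced within strata**, which the stated aim of even recruitment may suggest. Between-stratum variation then stays in the variance of the plain test although the design has removed it from the comparison, so the test becomes conservative.

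A further risk is that, with nothing prespecified, the choice between an adjusted and an unadjusted result could be made after the data are seen.

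**Working it through.** **Inputs from the documents.** 50 dyads, 25 per arm (Section 1.0, Aim 1); control concordance 50%, video 89%, stated power 80% (Data Analyses, Aim 1). The text calls this a 41% difference, but 89 - 50 = 39 points; the two rates are used here.

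**Assumptions.** Two-sided 5% level (none is stated). Stratum shares and concordance rates by stratum (none is given). Blocks of 4 wherever balance within strata is examined.

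**Step 1: the plan's own figure.** Exact binomial enumeration with 25 per arm, 50% vs 89%:

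- uncorrected Pearson chi-square: 89.1%
- continuity-corrected chi-square: 80.1%
- Fisher: 80.3%

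The stated 80% reproduces with the corrected or exact test. The plan does not say which form of chi-square is meant.

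**Step 2: discreteness alone.** With 50% concordance in both arms of 25 and no strata at all, exact type I error is 6.5% for Pearson and 3.3% for the corrected test. Departures from 5% of this size need no stratum effect.

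**Step 3: adding strata.** In stratum s, let n1 and n0 be the arm sizes, n their sum, x1 the concordant dyads in the video arm and m all concordant dyads. Then

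CMH = [Σ(x1 - n1·m/n)]² / Σ[n1·n0·m·(n - m) / (n²(n - 1))], rejecting above 3.84.

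Simulation used 200,000 trials per scenario. Overall concordance is 50% in both arms for error, and 50% vs 89% for power. Neither test has a continuity correction.

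Type I error (%), Pearson / CMH:

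| Assumed strata (control concordance) | Simple, as written | Blocks of 4 |
|---|---|---|
| 70/30, no difference | 5.7 / 4.9 | 6.5 / 5.0 |
| 70/30, 20 points apart | 5.7 / 4.9 | 6.2 / 5.2 |
| 70/30, 40 points apart | 5.7 / 4.9 | 4.7 / 5.0 |
| 50/50, 40 points apart | 5.7 / 5.0 | 4.5 / 5.0 |
| 50/50, 60 points apart | 5.7 / 4.8 | 2.2 / 4.9 |
| Four uneven strata | 5.6 / 4.9 | 5.6 / 4.9 |

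Under simple randomisation the Pearson error does not move with the stratum effect; the corrected test is at about 2.8% throughout. Under blocking, the Pearson error falls as the stratum effect grows.

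Power (%), Pearson / CMH:

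| Assumed strata | Simple, as written | Blocks of 4 |
|---|---|---|
| 70/30, no difference | 88.2 / 87.0 | 89.3 / 88.3 |
| 70/30, 20 points apart | 88.1 / 87.8 | 89.6 / 89.1 |
| 70/30, 40 points apart | 88.2 / 90.7 | 90.6 / 91.9 |
| 50/50, 60 points apart | 88.3 / 94.0 | 91.9 / 94.9 |
| Four uneven strata | 88.5 / 87.2 | 90.1 / 89.9 |

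The change runs from about -1 point to about +6 (94.0 - 88.3 = 5.7).

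**Step 4: trials that happen to be imbalanced.** This used 400,000 null trials per case, simple allocation and assumed strata of 35 and 15 dyads. In about 14% of trials the arms differ by 20 points or more in stratum mix.

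| Imbalance in stratum mix | Pearson error, concordance 59%/29% | Pearson error, concordance 65%/15% |
|---|---|---|
| 20 to 30 points | about 8% | about 12% |
| 30 points or more (2.4% of trials) | about 11 to 12% | about 21% |

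CMH stays at about 5% in these trials. If the strata are unrelated to concordance, Pearson stays near 5.7% whatever the imbalance.

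**The case against.** The strongest reply is that an unadjusted test is valid here. Simple randomisation within strata, without blocks, is equivalent to unstratified simple randomisation, and Step 3 confirms that the test's overall error then does not depend on the strata. The documents offer no evidence that race or ethnicity predicts concordance. Section 2.0 reports a link with dying in hospital, which is a different outcome. With 50 dyads, splitting by both race and ethnicity could leave nearly empty cells, and a weakly prognostic factor costs CMH a little power. All of this stands, and it keeps the point modest.

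Two stronger readings are tempting, and the documents support neither.

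- **A reader might infer that ignoring the strata inflates false positives or makes the error rate drift from 5%.** Overall, the excess above 5% is discreteness and is present with no stratum effect. If the arms are balanced within strata, ignoring the strata only lowers the error. Higher error appears only conditionally, in trials with a marked chance imbalance and a prognostic factor.
- **A reader might set the stated 80% against the 87% to 95% of CMH and call the gap lost power.** That compares a corrected test with an uncorrected one. In the first simple-randomisation scenario, dropping the correction takes power from 80.1% to 88.2% (+8.1 points), and stratifying then takes it to 87.0% (-1.2 points).

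It would also go too far to say that every planned analysis ignores the factor. Aim 2 names no test, and the covariate list of the exploratory regression is open-ended.

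What the reply does not remove is the mismatch between design and analysis, the lack of protection against imbalance in the one trial that will be run, and the missing definition of the strata.

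**Conclusion.** The mismatch is real and its consequences are moderate. No between-arm test named under Data Analyses uses the stratification factor. Under the allocation as written, overall type I error is unaffected, but a chance imbalance in a prognostic stratum would go uncorrected. Under balanced allocation, the plain test turns conservative as the strata become more prognostic, down to 2.2% in the most extreme assumed case. CMH stays between 4.8% and 5.2% throughout, for a like-for-like power change of about -1 to about +5 or +6 points. A material gain needs strongly prognostic strata.

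All stratum shares, concordance rates by stratum and block sizes are assumptions, as is the two-sided 5% level. The range, rather than any single figure, is the result. The case for changing the plan rests on matching the analysis to the design at almost no cost.

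**What to change.** 1. In Section 7.0 (Randomization), define the stratum levels, state whose race and ethnicity in the dyad counts, and state whether blocks are used. As it stands, simple allocation and the aim of even recruitment are hard to reconcile.
2. Under Data Analyses, Aim 1, make the primary test a CMH test without continuity correction, stratified by that factor. Prespecify a rule for collapsing sparse strata, for example to two levels. Report the Mantel-Haenszel risk difference with its 95% CI.
3. Keep the unstratified chi-square as a sensitivity analysis and say whether it is continuity-corrected.
4. For the continuous outcomes, replace the plain t or Wilcoxon test with linear regression including the same factor, or with a stratified rank test. A covariate cannot simply be added to the existing tests.
5. Restate the primary power for the test chosen.

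The cost is a few sentences and no new data, since race and ethnicity are already collected. The downside is about 1 point of power if the factor is not prognostic, and the need to collapse strata at 50 dyads.
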